### **3.2 Off study criteria for the study**

1. Request by the patient at any time for any reason.
2. The patient may at any time be removed from the trial at the principal investigator's discretion if the principal investigator deems the patient to be at unacceptable risk to remain on the study. Reasons for this action may include (but are not limited to) disease progression with declining organ function/performance status before treatment; inadequate family/caregiver support; noncompliance.

### **3.3 Off treatment criteria for the study**

1. Unacceptable adverse event(s) due to the infusion of any of the three antineoplastic agents which necessitates the termination of the therapy.
2. Intercurrent disease that prevents the administration of treatment.

## **4.0 ON STUDY EVALUATION**

All patients enrolled in the study will have the following evaluations:

1. History and physical examination will be performed daily during the hospital stay and then weekly ( $\pm$  4 days) as an outpatient for 4 weeks after discharge and then every 2 weeks until count recovery (defined as ANC  $\geq$ 1000 with or without PLT  $\geq$  100,000). Daily weight will be measured (if clinically possible) while in the hospital and at each outpatient visit.
2. If patients develop grade 3 or 4 non-hematologic toxicity during their treatment, they will be followed weekly after discharge until resolution of toxicity or improvement to grade 2 or less.
3. CBC with differential, complete metabolic panel (Na, K, Cl, CO2, glucose, BUN, Cr, Ca, total protein, albumin, total bilirubin, AST, ALT, and alkaline phosphatase), phosphorus, uric acid, magnesium level and LDH will be performed daily while in the hospital. After discharge, CBC with differential and complete metabolic panel as defined above will be obtained weekly ( $\pm$  4 days) until count recovery (defined as ANC  $\geq$ 1000 with or without PLT  $\geq$  100,000).
4. Bone marrow biopsy and/or aspirate will be performed no earlier than 7 days after the therapy completion to evaluate disease response.
5. Bone marrow biopsy/aspiration to test for remission will be performed once hematopoietic recovery (defined as ANC  $\geq$ 1000 with or without PLT  $\geq$  100,000) has been achieved. It can be performed in the inpatient or outpatient setting. If the bone marrow is consistent with morphologic complete remission, minimal residual disease testing will be performed with flow cytometry. If, on diagnosis, the NPM1 mutation was detectable by PCR or next-generation sequencing, then NPM1 PCR will be performed as well if morphologic complete remission is achieved. If hematopoietic recovery has not been achieved by 5 weeks ( $\pm$  7 days) after the completion of therapy, bone marrow biopsy and/or aspiration for disease evaluation will be

performed. If there is no evidence of leukemia, subsequent bone marrow biopsies will be performed based on count recovery.

6. After the assessment of the recovery marrow patients will be followed remotely from chart review to evaluate the disease-free survival and the overall survival. If information cannot be obtained from the chart patients may be contacted by telephone.

## **5.0 STATISTICAL CONSIDERATIONS AND METHODOLOGY**

### **5.1 Number and evaluable of patients**

This is a phase II study of the combination therapy of GO, mitoxantrone and etoposide as second line therapy in patients with acute myeloid leukemia. The study is designed to assess the therapeutic efficacy and the toxicity profile using Simon's optimal two-stage phase II design to permit early stopping of the trial if there is strong evidence that the studied treatment is ineffectual.

To be evaluable for clinical response, a patient must:

1. Receive a total of 5 days of mitoxantrone and etoposide,
2. Receive 1 dose of GO and
3. Have a follow-up bone marrow biopsy to evaluate the response to therapy.

Additional participants will be recruited to replace those who are not evaluable for clinical response. The accrual target is a maximum of 44 response-evaluable patients. All participants who begin treatment will be counted in the interim analysis for excess mortality.

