### **5.2. Sample Size/Accrual rate**

#### **5.2.1 Sample size**

This study is expected to require a minimum of 16 patients (at the interim evaluation of response) and a maximum of 44 response-evaluable patients unless undue toxicity is encountered. We anticipate accruing up to 9 additional patients (~20%) to account for patients who may prove unevaluable (i.e. ineligibility, cancellations, death or major violations). Therefore, our overall sample size will be a maximum of 53 patients.

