### **5.3. Study design**

**5.3.1 Definition of complete remission (CR):** An evaluable patient will be classified as having complete remission if they meet the criteria in Appendix II.

**Decision Rule (Simon two-stage design):** The largest CR rate where the proposed treatment regimen would be considered ineffective in this population is 35%. Subsequent studies will be warranted if the CR rate is 50% or higher or the CR rates are similar to historical data but

the disease-free survival and the overall survival are improved in comparison to our institution's historical cohort. The following optimal Simon two stage design uses 44 patients to test the null hypothesis that the true CR rate in the given patient population is at most 35%.

**Stage 1:** Enter 16 evaluable patients. If 5 or fewer patients have a CR in this timeframe, we will consider this early evidence that this treatment regimen is not sufficiently efficacious in this patient population, and the accrual of patients will be stopped. If 6 or more patients have a CR, then accrual will continue in the second stage of this trial.

**Stage 2:** Enter an additional 28 evaluable patients to the trial. If 19 or more patients achievea complete remission, the treatment will be promoted for further consideration. This design has  $\alpha=0.15$  and  $\beta=0.20$ ; the large value of  $\alpha$  is appropriate in an early phase trial. If the probability of CR is 35%, the expected sample size is 30.3 patients, i.e., the probability that the trial will be halted after 16 patients is 48.9%.

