### **5.3.2 Monitoring for treatment-induced mortality**

The trial will be continually monitored to ensure that treatment-induced mortality is not excessive, defined as  $>0.20$  of patients treated. A safety-evaluable patient is a patient

who was consented and started the protocol chemotherapy. All safety-evaluable patients, not just those evaluable for clinical response, are counted in the interim analysis for mortality. The cutpoints are listed in Table 2.

**Table 2.** Stopping rule for excessive mortality. The trial will be halted if, for the number of patients in the following table, the number of deaths is greater than or equal to the given number.

# Patients	# Deaths	# Patients	# Deaths
4	3	24	7
6	3	26	8
8	3	28	8
10	4	30	8
12	4	32	9
14	5	34	9
16	5	36	10
18	6	38	10
20	6	40	11
22	7	42	11

Justification of the stopping rule: It was assumed that under standard of care, the probability of death is  $\pi=0.2$ . A beta-binomial model is assumed with  $\alpha=2$  and  $\beta=8$ . If the number of deaths,  $x$ , is greater than the value in the Stopping Rule table for the number of patients,  $n$ , then:

$$P(\pi>0.2|\alpha,\beta,x,n)>0.75.$$

Under different assumptions of the true probability of death (True P(Death)), the expected number of patients ( $E(n)$ ) and the probability of the trial stopping early ( $P(Stop Early)$ ) were determined by Monte Carlo simulation:

True P(Death)	E(n)	P(Stop Early)
0.20	28.3	0.513
0.25	22.9	0.720
0.30	15.8	0.900
0.35	11.5	0.973
0.40	8.4	0.994
0.45	6.9	0.996

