## 5.4. Statistical analysis plan

### 5.4.1. Analysis of complete remission

The probability of complete remission (CR, Appendix II) will be estimated by the number of CR divided by the total number of patients evaluable for response. A 95% one-sided exact binomial confidence interval of the form  $(\pi_{\text{L}}, 1)$  for the true probability of CR will be calculated.

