## **8. STUDY EVALUATION, TREATMENT SCHEMA AND FLOW CHART**

Pre-treatment evaluation	
	Within last 6 weeks from day of consent
Anti-Hepatitis C antibody and if positive HCV RNA PCR	X

Hepatitis B surface antigen	X
	Within 14 days from day of consent
Medical history and physical examination	X
Height, weight, BSA, ECOG performance status	X
Toxicities from prior therapies	X
Cardiac echocardiogram	X
Bone marrow biopsy and aspiration	X
Urine $\beta$ HCG in women $\leq$ 60 years old (pregnancy test)	X
PT/INR, PTT	X
Complete metabolic panel (Na, K, Cl, CO 2 , glucose, BUN, Cr, Ca, total protein, albumin, total bilirubin, AST, ALT and alkaline phosphatase)	X
Magnesium, Phosphorous, Uric Acid, LDH	X
CBC with differential	X
Urinalysis	X
Electrocardiogram (12 lead)	X
Chest radiograph	X
CT Chest, Abdomen and/or Pelvis if indicated	X

Treatment Schema						
	Day 1	Day 2	Day 3	Day 4	Day 5	Day 6
Mitoxantrone	X	X	X	X	X	
Etoposide *	X	X	X	X	X	
Gemtuzumab ozogamicin **						X

\* Dose modification of etoposide for patients who develop elevated total bilirubin and/or AST or decrease in creatinine clearance

Adverse event	Dose modification of etoposide
CrCl 10 – 50 ml/min	administer 75% of normal dose
CrCl < 10 ml/min	administer 50% of normal dose
CrCl <50 ml/min AND Total bilirubin >3 mg/dL or AST >3 times ULN	Hold etoposide

\*\*If enrolled patients on day 6 of therapy have levels of aspartate aminotransferase (AST)  $\geq 2.5 \times$  UNL or alanine aminotransferase (ALT)  $\geq 2.5 \times$  UNL or total bilirubin  $\geq 2 \times$  ULN the administration of GO will be on hold until recovery of total bilirubin to less than or equal to  $2 \times$  ULN and AST and ALT to less than or equal to  $2.5 \times$  ULN prior to each dose. Daily values of LFTs will be obtained. The GO dose can be delayed up to the 10th day after the initiation of therapy due to toxicity or unexpected events (ie infection). Doses of GO will be capped at 4.5mg. Administration of a FLT3 inhibitor will be prohibited until CR is achieved. The use of a FLT-3 inhibitor is not prohibited after CR has been achieved for patients with FLT3-ITD or FLT-TKD mutations.

ON STUDY EVALUATION	TIMING
History and physical examination	Daily during the hospital stay at UPMC Shadyside Hospital and then weekly as outpatient for 4 weeks, and then every 2 weeks until count recovery

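### The primary CR analysis replaces treated patients who die before a follow-up marrow or do not complete the regimen, so it can overstate CR per treated patient, and no all-treated CR analysis is planned

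*Combined protocol and SAP*

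**What the plan says.** Section 5.1 sets three conditions for response evaluability: all five days of mitoxantrone and etoposide, one dose of GO, and a follow-up marrow. It then provides: "Additional participants will be recruited to replace those who are not evaluable for clinical response". Section 5.2.1 adds up to 9 patients to the 44, "to account for patients who may prove unevaluable (i.e. ineligibility, cancellations, death or major violations").

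The same set carries the decision and the estimate. Section 5.3.1 counts evaluable patients in stage 1 (16) and in stage 2: "Enter an additional 28 evaluable patients to the trial". Section 5.4.1 estimates CR "by the number of CR divided by the total number of patients evaluable for response". The null rate is introduced with "The largest CR rate where the proposed treatment regimen would be considered ineffective in this population is 35" (per cent). No source is given for it, and the text does not say whether it is a rate per treated or per evaluable patient.

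The plan does define an all-treated set, but uses it only for the mortality rule in section 5.3.2: "All safety-evaluable patients, not just those evaluable for clinical response, are counted in the interim analysis for mortality".

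**The concern.** Exclusion happens after treatment has started and can depend on its outcome. A patient who dies before the follow-up marrow is certainly not a CR, but is taken out and replaced by someone who may be one. Two other routes out are less clear-cut. Section 3.3 ends treatment for "Unacceptable adverse event(s) due to the infusion of any of the three antineoplastic agents which necessitates the termination of the therapy". Section 8 has holds for etoposide and for GO ("the administration of GO will be on hold until recovery of total bilirubin"). Patients lost in these ways may or may not reach CR.

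If excluded patients do worse, the CR rate and its exact lower confidence limit are too favourable as statements about treated patients. If 35% was also meant per treated patient, the CR rule lets an ineffective regimen through more often than the design states. The last line under partial remission in Appendix II treats patients who do not reach CR as failures, but nothing carries this into the denominator for those without a marrow.

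**Working it through.** **1. The plan's own figures.** Inputs from 5.3.1: stop if at most 5 CRs in 16; go if at least 19 in 44.

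P(go | p) = sum over x = 6 to 16 of Bin(x; 16, p) × P(Y ≥ 19 − x), with Y ~ Bin(28, p).

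This gives 0.142 at p = 0.35 and 0.801 at p = 0.50. The early-stop probability at 0.35 is 0.490 and the expected size is 16 + 28 × 0.510 = 30.3. The design is reproduced, and alpha of 0.15 is correct for evaluable patients.

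**2. Bias in the CR rate.** Let q be the share of treated patients excluded and c their CR probability, both assumptions. With a true rate of 35% per treated patient, the expected evaluable-only rate is (0.35 − qc)/(1 − q). With c = 0:

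- q = 3%: 0.35/0.97 = 36.1%
- q = 5%: 0.35/0.95 = 36.8%
- q = 10%: 0.35/0.90 = 38.9%

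Put through the Simon rule alone, these give P(go) of 0.178, 0.206 and 0.292. With c = 0.20, P(go) is 0.168 at q = 5% and 0.199 at 10%. With c = 0.35 it stays at 0.142.

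**3. Adding Table 2 and the 53-patient cap.** This was simulated with at least 300,000 trials per setting (standard error below 0.001). Overall CR is fixed at 35% per treated patient. A death before the marrow is excluded and replaced; a later death is evaluable and not a CR. At most 53 patients are treated. Table 2 is checked at each listed number of patients, with deaths known at once. Go requires passing stage 1, at least 19 CRs and no mortality stop.

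Two values of total mortality are used. The 14% is taken from the infectious deaths in the retrospective series in section 1.2, and the 20% is the standard-of-care assumption in 5.3.2. The documents do not give the share dying before the marrow, so a range is shown.

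| Die before marrow | P(go), 14% total deaths | P(go), 20% total deaths |
|---|---|---|
| 2% | 0.150 | 0.12 |
| 3% | 0.160 | 0.13 |
| 5% | 0.184 | 0.145 |
| 10% | 0.251 | 0.19 |
| All treated counted, no replacement | 0.131 | 0.108 |

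The value 0.15 is passed above about 2% in the first column and only at about 6% in the second, because Table 2 then halts more trials.

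**4. Upper scenario.** Suppose every exclusion is an early death and no evaluable patient dies. P(go) is 0.204 at 5% and about 0.27 at 10%. At 14% and 17% it is 0.31 and 0.31 if go is allowed with fewer than 44 evaluable patients when the cap is reached, or 0.28 and 0.24 if 44 must be reached. The 17% is 9/53, the whole allowance.

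**5. What 19 CRs mean per treated patient.** 19/44 = 43.2% with no replacement; 19/49 = 38.8% if five treated non-CR patients are replaced; 19/53 = 35.8% if nine are.

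**The case against.** The strongest reply is that the rates were meant per evaluable patient. Section 5.3.1 opens by defining CR for an evaluable patient, both stages count evaluable patients, and 5.4.1 estimates the CR probability from them. That is the more natural reading, and on it alpha is 0.142 with no inflation. What remains is that the plan never says so and gives no source for 35%. The nearest benchmark, 13 of 35 (37%) in section 1.2, is described over treated patients, and how incomplete courses or missing marrows were handled there is not stated.

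The size of the effect is also uncertain. The timing of the 14% infectious deaths is not given. The follow-up marrow may be done from 7 days after therapy, and deaths after it stay in the denominator. The five earlier patients in section 1.2, who had fewer mitoxantrone days, had no treatment-related deaths. The allowance of 9 also covers ineligibility and cancellations, and omitting patients who never start treatment does not cause this bias. All of this stands, and it limits the size rather than the direction.

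The evaluable set is openly prespecified, alpha was deliberately liberal, and deaths are visible through Table 2, treatment-related mortality and overall survival. These points lower the severity. They show the deaths but do not correct the CR denominator.

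**Conclusion.** The concern holds in conditional form. The evaluable-only rate overstates CR per treated patient whenever excluded patients reach CR less often, by about 1 to 4 percentage points for 3% to 10% excluded with no CR. Nothing planned would show this.

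A reader might infer more than the documents support:

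- **That the stated alpha is wrong.** It is correct per evaluable patient. It is exceeded only if 35% is per treated patient, excluded patients do worse, and enough of them die before the marrow.
- **That a 2% exclusion rate always breaks 0.15.** This depends on 14% total mortality. At the plan's own 20% the crossing is at about 6%.
- **That the false-go chance is above 0.30.** This needs every exclusion to be an early death at 14% or more, and a go without 44 evaluable patients.

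If exclusion is unrelated to CR, there is no inflation. The figures concern the CR rule only; 5.3.1 also allows further study on improved survival with CR similar to historical data. Severity: should-fix, as a cheap improvement.

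**What to change.** - For both Simon counts (16, then 44) and for 5.4.1, use every eligible patient who starts protocol chemotherapy. This is the safety-evaluable set of 5.3.2 restricted to eligible patients.
- Count early deaths and all other patients without a documented CR as non-CR.
- Replace only patients who never start treatment or are found ineligible.
- Report the evaluable-only CR rate as a sensitivity analysis.
- State in 5.3.1 that 35% and 50% are rates per treated patient, and give the source of 35%.

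The cost is wording in 5.1, 5.2.1, 5.3.1 and 5.4.1, no added enrolment, and a slightly lower reported CR rate.

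Power needs an honest statement. Under the Simon rule alone it stays at 0.80 if 50% is per treated patient. If 50% was meant per evaluable patient, the per-treated rate is 0.50 × (1 − q), and power is about 0.75, 0.71 and 0.59 at 3%, 5% and 10% excluded. With Table 2 included, 50% CR per treated patient and 5% dying before the marrow, P(go) is about 0.70 under the fix against 0.75 under the plan at 14% total deaths, and 0.50 against 0.52 at 20%. The fix therefore lowers the chance of go somewhat under the target rate as well as under the null.

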### **5.2. Sample Size/Accrual rate**

#### **5.2.1 Sample size**

This study is expected to require a minimum of 16 patients (at the interim evaluation of response) and a maximum of 44 response-evaluable patients unless undue toxicity is encountered. We anticipate accruing up to 9 additional patients (~20%) to account for patients who may prove unevaluable (i.e. ineligibility, cancellations, death or major violations). Therefore, our overall sample size will be a maximum of 53 patients.

### **5.2.2. Accrual time and study duration**

Based on previous efforts in recruiting patients at the UPMC Hillman Cancer Center, it is anticipated that at least thirty patients per year will be enrolled in the protocol and the accrual will be completed within two years. The final evaluation of the study to assess overall survival will be conducted at 5 years or if all subjects expire, whichever comes first.

### **5.3. Study design**

**5.3.1 Definition of complete remission (CR):** An evaluable patient will be classified as having complete remission if they meet the criteria in Appendix II.

**Decision Rule (Simon two-stage design):** The largest CR rate where the proposed treatment regimen would be considered ineffective in this population is 35%. Subsequent studies will be warranted if the CR rate is 50% or higher or the CR rates are similar to historical data but

the disease-free survival and the overall survival are improved in comparison to our institution's historical cohort. The following optimal Simon two stage design uses 44 patients to test the null hypothesis that the true CR rate in the given patient population is at most 35%.

**Stage 1:** Enter 16 evaluable patients. If 5 or fewer patients have a CR in this timeframe, we will consider this early evidence that this treatment regimen is not sufficiently efficacious in this patient population, and the accrual of patients will be stopped. If 6 or more patients have a CR, then accrual will continue in the second stage of this trial.

**Stage 2:** Enter an additional 28 evaluable patients to the trial. If 19 or more patients achievea complete remission, the treatment will be promoted for further consideration. This design has  $\alpha=0.15$  and  $\beta=0.20$ ; the large value of  $\alpha$  is appropriate in an early phase trial. If the probability of CR is 35%, the expected sample size is 30.3 patients, i.e., the probability that the trial will be halted after 16 patients is 48.9%.

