## **1.0 INTRODUCTION**

### **1.1 Study objectives**

Primary Objective: To evaluate the response rate and toxicity of the combination of mitoxantrone, etoposide and gemtuzumab ozogamicin as second line therapy in patients with acute myeloid leukemia (AML) who have failed the first induction therapy.

Secondary Objectives: To assess the progression-free survival, overall survival and treatment related mortality in patients with AML treated with the combination of mitoxantrone, etoposide and gemtuzumab ozogamicin.

To explore if age, cytogenetic status, percent of blast in the bone marrow prior to therapy or percent expression of CD33 in the leukemia blasts are predictive of complete remission, overall survival or progression-free survival in patients with AML treated with the combination of mitoxantrone, etoposide and gemtuzumab ozogamicin.

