### 5.4.2 Analysis of secondary endpoints

Overall and progression-free survival functions will be estimated by the product limit (Kaplan-Meier) method. The median survival and its 90% confidence interval will also be reported.

Proportional hazards (Cox) regression will be used to describe the relationship between age, cytogenetic status (poor, intermediate, favorable), percent of blast in the bone marrow prior to therapy and percent expression of CD33 in the leukemia blasts to overall and progression-free survival. Likelihood ratio tests will be used to identify statistically significant ratios and profile likelihood confidence intervals will be estimated for hazard ratios of statistically significant predictors. Logistic regression will be applied in a similar fashion to determine predictors of complete remission.

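### Does the survival-versus-historical clause in the Decision Rule make the stated alpha of 0.15 and beta of 0.20 misleading?

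*Combined protocol and SAP*

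**What the plan says.** Section 5.3.1 sets a Simon optimal two-stage design with 44 evaluable patients "to test the null hypothesis that the true CR rate in the given patient population is at most 35" per cent.

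- **Stage 1.** With 5 or fewer CRs in 16, accrual stops and "we will consider this early evidence that this treatment regimen is not sufficiently efficacious".
- **Stage 2.** With 19 or more CRs in 44, "the treatment will be promoted for further consideration".
- **Error rates.** Alpha 0.15 and beta 0.20 are stated straight after these cuts, as properties of this design.

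The same Decision Rule paragraph contains a wider sentence, which offers a second ground for further study. On that ground CR need only resemble the historical rate, provided that "the disease-free survival and the overall survival are improved in comparison to our institution's historical cohort".

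Elsewhere, survival is secondary and descriptive. The objective in 1.1 is "To assess the progression-free survival, overall survival and treatment related mortality", and 5.4.2 says "Overall and progression-free survival functions will be estimated by the product limit (Kaplan-Meier) method". Section 4.0 uses a different term: "patients will be followed remotely from chart review to evaluate the disease-free survival and the overall survival".

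**The concern.** The two grounds for further study are joined by *or*. Only the first has a sample size, a cut and error rates. For the second:

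- *similar* and *improved* are not defined, and no time point is set;
- the historical cohort is not named in 5.3.1, and the 35-patient institutional series in 1.2 is reported without disease-free or overall survival;
- disease-free survival is never defined, and 5.4.2 analyses progression-free survival instead;
- 5.4 plans no comparison with historical data.

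A reader could take 0.15 as the full risk of promoting a regimen whose true CR rate is 35% and whose survival is no better than before. If a trial that misses 19 of 44 can be rescued by an informal historical comparison, that risk is higher than 0.15 suggests. The comparator and endpoint could also be picked after the data are seen.

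**Working it through.** **Inputs.** From 5.3.1: null CR rate 0.35, alternative 0.50, stop at 5 or fewer of 16, promote at 19 or more of 44. From 1.2: 13 of 35 CRs (37%) and 14% infectious deaths in the institutional series. From 5.3.2: the Table 2 mortality cuts and a reference death probability of 0.20.

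**Step 1: reproduce the plan's figures.** Let X1 be the number of CRs in 16 and X2 the number in the next 28.

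- P(stop at stage 1) = P(X1 ≤ 5) = 0.490 at 0.35 (plan: 48.9%).
- Expected size = 16 + 28 × (1 − 0.490) = 30.3 (plan: 30.3).
- P(promote) = Σ over x = 6 to 16 of P(X1 = x) × P(X2 ≥ 19 − x) = 0.142 at 0.35 and 0.801 at 0.50.

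Both stated limits are met. A final cut of 18 would give alpha 0.207 and a cut of 20 would give power 0.736, so 19 is the right cut.

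**Step 2: is 50% an observed threshold?** The cut 19/44 is 43%. Requiring an observed 50% (22/44) would give alpha 0.028 and power 0.545, which are not the stated values. So 50% is the design alternative, and Stage 2 gives the operating cut.

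**Step 3: what the survival route could add.** At 0.35, P(pass stage 1, miss 19) = 1 − 0.490 − 0.142 = 0.368. Let q be the chance that survival looks improved when it is not. The documents give no value, so q = 5% to 15% is an assumption, as is independence from the CR count. Assume also that the route is closed after a stage 1 stop.

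- Total = 0.142 + 0.368q, which is 0.160 to 0.197. It passes 0.15 at q = 2.2%.
- If *similar* is taken as within 5 points of 37% (an assumed margin), only 15 to 18 CRs of 44 qualify, with probability 0.269. Total = 0.142 + 0.269q, which is 0.155 to 0.182. It passes 0.15 at q = 3.0%.

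**Step 4: include the mortality rule.** Step 3 lets every trial run to its CR conclusion, but 5.3.2 can halt it first. Apply the Table 2 cuts exactly (stop when deaths reach the listed number), with 44 treated patients and deaths independent of CR. Each probability in the unlimited version of Step 3 is then multiplied by 1 − P(mortality stop).

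| Death probability | P(mortality stop) | CR route alone | Total, q = 5% to 15% | q needed to pass 0.15 |
|---|---|---|---|---|
| none (Step 3) | 0 | 0.142 | 0.160 to 0.197 | 2.2% |
| 0.14 | 0.162 | 0.119 | 0.134 to 0.165 | about 10% |
| 0.20 | 0.438 | 0.080 | 0.090 to 0.111 | about 34% |

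For the last row: 0.142 × 0.562 = 0.080, 0.368 × 0.562 = 0.207, and (0.150 − 0.080)/0.207 = 0.34. The plan's own simulated stop probability at 0.20 is 0.513. That gives 0.069 for the CR route, 0.179 for the stage 2 misses, and (0.150 − 0.069)/0.179 = 0.45.

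**The case for a change.** The strongest case for a change does not need the illustrative rates. A second route joined by *or* can only raise the chance of further study, and the plan neither states nor limits the rise. The sponsor chose to give error rates for this decision and defended a large alpha, so readers may take 0.15 as the risk of the whole rule. A sentence labelling the survival comparison as supportive would need no patients and would leave 6/16 and 19/44 unchanged. If the survival route stayed open after a stage 1 stop, which the text does not expressly exclude, the total without the mortality rule would be 0.142 + 0.858q, or 0.185 to 0.271 for the same q.

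What stands is the direction of the effect and the lack of definitions: *similar*, *improved* and disease-free survival are unspecified, and no historical comparison is planned. The following does not stand.

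- **No stated number is wrong.** Alpha and beta follow the CR cuts and are tied to a CR null hypothesis. Saying that they apply to the CR count restates the text.
- **The stage 1 reading is strained.** Section 5.3.1 treats 5 or fewer CRs as evidence of insufficient efficacy and stops accrual.
- **The cohort is not in real doubt.** Section 1.2 describes one institutional series on mitoxantrone and etoposide alone and cites its publication. The only other institutional data there are five patients who received the study drug, an unlikely comparator.
- **Demoting the clause has a cost.** A regimen that lengthens survival without raising CR would lose its route forward. Table 1 lists gemtuzumab trials with improved event-free, disease-free or overall survival, so the sponsor had reason to keep that route open.

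**Conclusion.** The concern does not call for a change. The CR design is sound and its error rates are correctly stated for the test they describe (exact alpha 0.142, power 0.801). The survival clause is loosely worded, but it is a planning judgement about whether later studies are worthwhile in a single-arm phase II trial. No efficacy claim rests on it.

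Its effect on the chance of a mistaken promotion is upward, but the documents do not allow it to be sized. The claim that it pushes the total past 0.15 is not robust. It depends on an assumed q, assumed independence and an assumed reading of *similar*, and it ignores the mortality stop. With that stop included, the q needed rises from 2.2% to about 10% or 34%, depending on mortality. These figures are themselves illustrative, since deaths and CR are unlikely to be independent. The clause also requires disease-free and overall survival both to improve, which a single q does not model.

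What remains is a choice between a strict CR-only rule and a rule that leaves room for a survival benefit. The sponsor chose the second, and either is defensible. Naming the series in 1.2, using the planned progression-free and overall survival curves, and reporting the comparison as descriptive are steps that a competent analyst would take without an amendment.
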